The measurement of vital parameters is essential for: assessing the patient's health status; follow the evolution of his state of health; check the effectiveness of the treatments; assist in medical diagnosis. In the state of this taking of vital signs includes the measurement of heart rate and respiratory rate.

Taking constants manually is now the reference in the hospital context, it consists of auscultating the patient by performing all the measurements manually with the help of tools such as a blood pressure cuff, a sangurometer or another thermometer. It is a time-consuming operation for the healthcare professional and may involve risks depending on the patient's profile, in particular the risk of infection and the risk of error.

Excluding respiratory constants, the taking of electronic constants is the most used by the medical profession, it is carried out thanks to multiparametric monitors in the vast majority of cases. A multi-parameter monitor is a medical device for monitoring a patient's vital parameters. Typically, basic models monitor heart activity, blood pressure, respiration, oxygen saturation, and temperature. They display the value of the parameters while presenting their evolution curves over time.

- Risk limitation

This solution differs from its competitors thanks to a feature that makes it its strength: the user has no physical contact with the camera, which is the only measurement tool. Nosocomial infections, or "care-associated infections", are infections contracted in a healthcare establishment such as a hospital or clinic. Santé Publique France estimates that approximately one hospitalized patient in 20 was confronted with it in France in 2017. The World Health Organization estimates on its website at 1.4 million the number of people who have contracted an infection with 'hospital. The Ministry of Health estimates that nosocomial infections are responsible for 4,000 deaths each year in France.

Other objectives are also targeted:

- Relieve medical and paramedical staff thanks to automated metrics taking.

- Secure and reassure patients through constant monitoring of their state of health
- Facilitate taking metrics without human intervention.

Details of the manufacturer of the investigational medical device

Name: Quantiq.io

Head office address (Kbis): [name]

Model/type name or number, including software version and accessories, if applicable, for complete identification.

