The name of the SaaS API is COBOX, a software-only solution.

As part of this study, we will use “COBOX” version 1.0.0.

During the clinical investigation, this API will be integrated into the “DemoCOBOX” version 0001 application in order to allow its use by medical personnel (or arc or tec) . This application will be installed on a Samsung S6 tablet. The tablet will be placed on a tablet support equipped with an anti-theft device.

Description of how traceability should be ensured during and after the clinical investigation, for example by assigning batch, batch or serial numbers.

During the clinical investigation, Quantiq.io will keep an identical model of the tablet with the same version of COBOX installed in order to be able to reproduce any possible deviation in a measurement and to investigate whether it comes from the tablet or the clinical trial conditions. The reference of each tablet distributed for the trial as well as the DemoCOBOX application version installed on it will be stored on our servers. The use of the application may be monitored on our servers. Quantiq reserves the right to make extremely minor patches to the API as well as the demo application during the trial, in order to meet a potential request from medical staff (or arc or tec) and/or patients. In the event of a bug fix, or non-substantial modification, the server may be put on hold. A system for updating the version on the “device” side can be used (telephone, pc).

The traceability of the software version used during the clinical investigation will be recorded on secure databases for the duration of the study and for a period of 10 years from the end of the study.

1. The populations and indications for which the experimental device is intended

COBOX is a medical software intended for the measurement of clinical parameters of heart rate and respiratory rate, in a medicalized or non-medicalized environment. COBOX is a solution intended to be used by healthcare personnel and lay users. As part of this test and in order to validate its performance, the COBOX device will be used by health professionals in real conditions of use.

As part of the study, the COBOX device is intended to be used:

- For measuring HR and RR in a clinical setting or at home for regular pathology monitoring or teleconsultation.
- In the context of reception and emergency care by trained personnel .
- On patients defined by the inclusion or exclusion criteria of this protocol.

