
QUANTIQ provides users with one tablet per site per physician. Delivery of a functional tablet in the event of a malfunction within 5 working days. Bug fix within 3 days in case of software malfunction with continuous information for professionals.

8. Research process

Research timeline

- Start of inclusions: Mid-July 2022
- Duration of the inclusion period: 2 months
- Duration of participation of each patient: The time of their passage in the IOA box (less than 30 minutes)
- Total research duration: 3 months

Summary of patient follow-up

- Oral information by the IOA. If necessary, an investigating physician can complete the information at the patient's request.
- Informed consent with electronic signature.
- Collection of the patient's age, gender and Fitzpatrick phototype.
- Collection of patient identification number.
- The nursing staff (or arc or tec) installs the oximeter on the patient's finger.
- The nursing staff (or arc or tec) starts COBOX and begins to count the breaths in parallel.
- After 15s, a first measurement is made by COBOX. The pulse oximeter reference result is acquired in parallel, associated with the patient ID number and stored with the COBOX result at the same time on an electronic database.
- After 20s (5s after the previous measurement), a second measurement is made by COBOX. The pulse oximeter reference result is acquired in parallel, associated with the patient ID number and stored with the COBOX result at the same time on an electronic database.
- After 25s (5s after the previous measurement), a third measurement is made by COBOX. The pulse oximeter reference result is acquired in parallel, associated with the patient ID number and stored with the COBOX result at the same time on an electronic database.
- After 30s, the nursing staff (or arc or tec) enters the number of breaths counted since the start. This result is converted into a respiratory rate (RR) then associated with the patient number and stored in the database.

The data is blocked on the database until the end of the study. At the end of the study, they will be sent to the coordinating centre.

In order not to disrupt the general operation of the emergency department and patient care, the usual patient circuit is not modified. The COBOX tool is used by the reception staff in a contemporary way to their usual collection of input parameters.

Collection of consent

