10. STATISTICAL ASPECTS

Study size calculation

Considering the results of the performance verification tests of the medical device under study, we have established the study hypotheses in connection with the calculation of the size of the study set out below:

Minimum acceptable value of the ICC correlation coefficient (ρ_0)	0.6
Expected value of the ICC correlation coefficient (ρ_1)	0.7
The number of observations per subject k	3
Two-sided significance level (α)	0.05
Power (1 - β):	90%
Minimum size (n)	226
Size at 30% safety margin	323

A final study size of 323 patients is retained; taking into account a rate of unusable data of 30% in order to maintain the statistical power of the study in the event of exclusion of outliers.

Statistical methods used

The analysis will carry an initial descriptive part. The qualitative variables will be expressed in frequencies (with their 95% CI), and the quantitative variables expressed in means (with their standard deviation) if the distribution is normal. Otherwise, the quantitative variables will be expressed as the median (with their interquartile range).

Then, we will perform a comparative analysis, using chi 2 tests (or Fisher's exact) for the qualitative variables and student test (or Mann-Whitney test if applicable) for the quantitative variables. For performance estimation, we will determine the intra-class correlation coefficient with its confidence interval and we will perform a graphical analysis of Bland and Altman. In addition, we will calculate the mean square errors between the measurement with COBOX and the reference measurements, and they will be expressed as a percentage.

All our analyzes will be carried out at the 5% significance level.

An analysis of the repeated and compared measurements between COBOX and the CE marked device (used during the technical reference process for taking measurements) for the heart rate will make it possible to evaluate the reproducibility of the COBOX on repeated measurements in the *COBOX Protocol Valid*

same individual. A secondary statistical analysis will be done for the measurement times T+5s and T+10s.

We will use imputation methods or sensitivity analysis for the management of missing data.

11. Access rights to source data and documents

Access to data

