- Verification of data collection with the tablet,
- The transmission of SAEs to the Sponsor.

He will work in accordance with standard operating procedures, in collaboration with the clinical research associate delegated by the Sponsor.

Quality control

A clinical research associate mandated by the sponsor visits each investigating center on a regular basis, during the setting up of the research, one or more times during the research depending on the rate of inclusions and at the end of the research. During these visits, the following elements will be reviewed:

- informed consent,
- Compliance with the research protocol and the procedures defined therein,
- Quality of data collected in the tablet: accuracy, consistency of data with source documents (medical records, appointment books, original laboratory results, etc.).

Any visit will be the subject of a monitoring report in written form.

Data management

Data processing will be carried out under the responsibility of [name].

The data will be entered automatically and stored in the tablet reserved for the study and provided by the sponsor.

The data validation and freezing processes will be carried out according to the procedures in force.

Auditing and inspection

An audit may be carried out at any time by persons appointed by the Sponsor and independent of the research managers. Its objective is to ensure the quality of research, the validity of its results and compliance with the law and regulations in force.

Investigators agree to comply with the requirements of the sponsor and the competent authority with respect to an audit or inspection of the research.

The audit may apply to all stages of the research: from the development of the protocol to the publication of the results and the classification of the data used or produced within the framework of the research.

13. Ethical and Regulatory Considerations

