 - All other documents and letters relating to the research

All these documents are the responsibility of the investigator for the regulatory archiving period.

– By the Sponsor:

- for a period of 15 years (research relating to drugs, medical devices or in vitro diagnostic medical devices or research not relating to a product mentioned in Article L.5311-1 of the Public Health Code),
 - The protocol and any amendments to the protocol
 - The original observation notebooks
 - A copy of the electronically signed informed consents of the participants
 - Documents relating to serious adverse events
 - All other documents and letters relating to the research

All these documents are under the responsibility of the Sponsor for the regulatory archiving period. No displacement or destruction can be carried out without the agreement of the Sponsor. At the end of the regulatory archiving period, the Sponsor will be consulted for destruction. All data, documents and reports are subject to audit or inspection.

15. Posting Rules

Scientific papers

The data provided by the investigating centers are centralized by the coordinating center and sent to Quantiq.io for statistical analysis (statistical analysis is done by Quantiq.io). This analysis gives rise to a written report which must then be sent to the Committee for the Protection of Persons and to the competent authority.

Any written or oral communication of the results of the research must receive the prior agreement of the coordinating investigator and, where applicable, of any committee set up for the research.

The publication of the main results mentions the name of the sponsor, of all the investigators who included or followed patients in the research, of the methodologists, biostatisticians and data managers who participated in the research, of the members of the committee(s) set up(s) for research and funding source(s). International rules for writing and publication will be taken into account (The Uniform Requirements for Manuscripts of the ICMJE, April 2010).

Communication of results to patients

In accordance with law n°2002-303 of March 4, 2002, patients are informed, at their request, of the overall results of the research.

Transfer of data

Data collection and management are handled by the coordinating centre. The conditions for the transfer of all or part of the research database are decided by the research sponsor and are the subject of a written contract.

Sponsor		COORDINATING INVESTIGATOR	

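### No rule keeps exclusions from the primary heart-rate ICC independent of COBOX-reference disagreement, and the manufacturer analyses the unmasked pairs

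*Combined protocol and SAP*

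**What the plan says.** **Who analyses.** Section 15 (Scientific papers) has the data "centralized by the coordinating center and sent to Quantiq.io for statistical analysis (statistical analysis is done by Quantiq.io"), and the resulting report goes to the ethics committee and the competent authority. Section 1 names Quantiq.io as sponsor and section 3 names it as manufacturer ("Name: Quantiq.io"). No second analysis is named.

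**What the analyst receives.** Under section 8 (Summary of patient follow-up), each oximeter reading is "stored with the COBOX result at the same time on an electronic database". No masking of either value is described.

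**What may be removed.** Section 10 (Study size calculation) sets 323 patients "taking into account a rate of unusable data of 30" per cent, and gives the possible exclusion of outliers as the reason. The only outlier procedure is the Dixon test in the section 1 summary, applied within the samples. Its variable, its level and the consequence of a positive result are not given, and section 10 does not mention it.

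**Controls that exist.** Section 8: "The data is blocked on the database until the end of the study", after which the data go to the coordinating centre. Section 15 (Transfer of data): "Data collection and management are handled by the coordinating centre". Section 12 (Data management): "The data validation and freezing processes will be carried out according to the procedures in force". Section 12 also allows an audit by people independent of the research managers, and section 15 requires the coordinating investigator's agreement before results are communicated.

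**A related activity.** Section 3 (traceability) has Quantiq.io keep an identical tablet "to reproduce any possible deviation in a measurement and to investigate whether it comes from the tablet or the clinical trial conditions".

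**The concern.** The primary endpoint is an agreement coefficient. Removing a session because the two devices disagreed removes part of the quantity being estimated, so the ICC rises whether or not the reason found for the removal is genuine. Poor light or movement may be equally present in sessions that happened to agree. If a fault is looked for mainly where readings differ, the flawed but concordant sessions stay in.

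The plan expects data to be removed after collection and leaves the criterion, the decision-maker and the information used for the decision open. The party that analyses the unmasked pairs has an interest in the result. At stake is the heart-rate ICC, the primary endpoint on which the validation rests.

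**Working it through.** **1. The plan's own figures.** Inputs from section 10: ρ0 = 0.6, ρ1 = 0.7, k = 3, two-sided α = 0.05, power 90%. The Walter-Eliasziw-Donner formula is

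n = 1 + 2k(z_α + z_β)² / [(k − 1)(ln C)²], with C = [1 + kρ0/(1 − ρ0)] / [1 + kρ1/(1 − ρ1)].

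- C = (1 + 4.5)/(1 + 7) = 0.6875 and (ln C)² = 0.1404.
- (1.960 + 1.282)² = 10.507.
- n = 1 + 6 × 10.507/(2 × 0.1404) = 225.5, so 226.
- 226/0.70 = 322.9, so 323.

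Both figures reproduce. The allowance is 323 − 226 = 97 sessions.

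**2. Exclusion unrelated to disagreement.** With a true ICC of 0.60, random removal of 1% to 30% leaves the mean ICC at about 0.60 and false success at about 2% to 4% (nominal 2.5%). The 30% allowance therefore costs precision but adds no bias.

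**3. Exclusion from among the discordant pairs.** Assumptions, none of them in the documents: normal errors of equal variance, one pair per patient, true ICC 0.60, n = 323, two-way single-measure ICC with F-based 95% limits, and success if the lower limit exceeds 0.60. There were 4,000 simulated trials per row. The shares reviewed and removed are also assumed.

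| Reviewed | Removed of those reviewed | Share of all sessions | Mean ICC | False success | Same share removed at random |
|---|---|---|---|---|---|
| none | none | 0 | 0.60 | about 2.5% | – |
| 10% most discordant | a quarter | 2.5% (8) | 0.63 | about 13% | 2-3% |
| 20% most discordant | a quarter | 5% (16) | 0.64 | about 20% | 2-3% |
| 20% most discordant | half | 10% (32) | 0.68 | about 67% | 2-3% |

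Repeat runs differ by about one or two percentage points. A separate simulation with a one-way ICC, dropping half of the 10% most discordant sessions (16), gave 40% false success with two readings per subject and 25% with three. The direction is the same and the size depends on the model.

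**4. Exclusion on raw heart rate.** This is one possible reading of the Dixon test. Under normal errors, dropping the sessions with extreme values lowers the ICC: 0.54 at 5% dropped and 0.50 at 10%. With heavy-tailed errors (assumed: 10% of sessions with a fourfold error SD; two readings), it raises the ICC to between 0.63 and 0.68 when 1% to 20% are dropped, and lowers it to 0.58 at 30%. The direction therefore depends on the variable tested and the error distribution.

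**The case against.** The strongest reply is that no passage provides for discordance-driven exclusion. A reader might infer from section 3 that the manufacturer looks for a cause only when a reading deviates, and then discards the session. The text does not support that. It is a traceability provision: it does not say that other readings go unchecked, does not mention exclusion or the analysis set, and does not give Quantiq.io the decision on usability. A reader might also infer that any exclusion under this plan favours the device. That fails for a Dixon test on raw heart rate, which can move the ICC either way.

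There are also safeguards: the block until study end, data management by the coordinating centre, validation and freeze, possible audit, and the coordinating investigator's agreement. They should be given weight, since they restrict access during the study and put another party in the chain. But the freeze procedure has no stated content, the audit is optional and carried out by sponsor appointees, and agreement to a communication is not a check of the analysis set. None of them says which sessions may be removed, or prevents removal after the pairs have been released.

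Finally, the percentages rest on assumed review shares, error distributions and a success rule. That is correct; they show sensitivity and do not predict what will happen.

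**Conclusion.** The point holds as a risk the plan leaves open. Up to 30% unusable data is budgeted for, the one named outlier test is unspecified, and the manufacturer analyses unmasked pairs with no rule separating exclusion from disagreement. To say that the primary ICC is, or will be, pushed upward would go beyond the documents.

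If exclusion did follow the paired difference, small numbers would matter. Removing 8 to 32 sessions, against an allowance of 97, takes false success from about 2.5% to about 13% to 67% for a device at the plan's minimum ICC. Those figures hold under the stated assumptions only. The size of the allowance is not itself the problem, because random loss up to 30% adds no bias. The change is a cheap improvement and worth making before the data are released.

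**What to change.** Amend section 10 (Statistical methods used) and section 15 (Scientific papers) as follows.

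1. The primary heart-rate ICC uses all sessions that have both a COBOX and a reference value.
2. A session may be excluded from it only for a fault on a list drawn up by the coordinating centre. The centre applies the same criteria to every session, uses information already recorded, does not see COBOX values or COBOX-reference differences, and signs the list before the data go to the sponsor.
3. Dixon exclusions, and causes found later through the section 3 investigation, appear only in a sensitivity analysis, with counts and reasons.

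The collection steps in section 8 list little beyond the readings, age, sex, phototype and identifier, with no record of signal quality, light or movement. The fault list will therefore be short, and no new data capture is needed. Because the list is made by the coordinating centre, the fix does not depend on withholding COBOX values from the sponsor, whose own software produces them.

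The cost is protocol wording and a little coordinating-centre time, since the paired values are stored together and a file without the COBOX values has to be prepared. No patients or study procedures are added. The drawback is that a genuine fault found late stays in the primary estimate. A re-run of the primary ICC by the coordinating centre would be a useful extra, but the fix does not need it.
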